6.4 Diet

For the course of the study, the patients will be instructed to maintain their normal diet and fluid intake as prescribed under their standard clinical care. They will be asked to avoid making significant changes in their diet during the study specially related to high oxalate foods and fluid intake.

The patients will be asked to refrain from ascorbic acid preparations or multivitamin preparations during the study. Vitamins given as standard of care for patients on dialysis are allowed during the study.

7 SELECTION AND WITHDRAWAL OF PATIENTS

7.1 Patient inclusion criteria

1. Signed informed consent (as applicable for the age of the patient). An appendix to the informed consent form will be signed by patients continuing on treatment after week 14.
2. Male or female patients \geq 2 years of age. Patients have to be able to swallow size 4 capsules twice daily, or use a gastric tube that allows for administration of size 4 capsules.
3. A diagnosis of PH (as determined by standard diagnostic methods).
4. Patient should be on a stable dialysis regimen for at least two weeks before baseline.
5. Plasma oxalate \geq 40 micromole/L prior to the dialysis session.
6. Patients receiving vitamin B6 must be receiving a stable dose for at least 3 months prior to screening and must remain on the stable dose during the study. Patients not receiving vitamin B6 at study entry must be willing to refrain from initiating vitamin B6 during study participation.

7.2 Patient exclusion criteria

7. Inability to swallow size 4 capsules twice daily, or using a gastric tube not suited for administration of size 4 capsules via the tube.
8. Ongoing treatment with immunosuppressive medication.
9. The existence of secondary hyperoxaluria, e.g. hyperoxaluria due to bariatric surgery or chronic gastrointestinal diseases such as cystic fibrosis, chronic inflammatory bowel disease and short-bowel syndrome.
10. Use of antibiotics to which *O. formigenes* is sensitive (see section 8.2.2), including current antibiotic use, or antibiotics use within 14 days of initiating study medication.
11. Current treatment with a separate ascorbic acid preparation. Standard of care vitamin supplement for patients on dialysis are allowed.
12. Pregnancy.
13. Women of childbearing potential who are not using adequate contraceptive precautions. Sexually active females, unless surgically sterile or at least 2 years post-menopausal, must be using a highly effective contraception (including oral, transdermal, injectable, or implanted contraceptives, IUD, abstinence, use of a condom by the sexual partner or sterile sexual partner) for 30 days prior to the first dose of OC5 and must agree to continue using such precautions during the clinical study.

14. Presence of a medical condition that the Principal Investigator considers likely to make the patient susceptible to adverse effect of study treatment or unable to follow study procedures.
15. Participation in any study of an investigational product, biologic, device, or other agent within 30 days prior to the first dose of OC5 or not willing to forego other forms of investigational treatment during this study.

7.3 Patient withdrawal criteria

If a patient fails to return for a scheduled study visit the investigator will make a reasonable effort to contact the patient and determine why the patient failed to return and to schedule a new study visit. Any information obtained during this contact will be documented in the study records.

A study patient will be discontinued from participation in the study if:

- Any clinical adverse event (AE), laboratory abnormality, illness, or other medical condition or situation occurs such that continued participation in the study would not be in the best interest of the patient.
- OxThera or the Principal Investigator in consultation with OxThera may discontinue the patient at any time for medical and/or administrative reasons.
- The patient withdraws consent from participating in the study at any time.
- The patient undergoes a transplantation procedure.
- There are major protocol violations.

Any patient who withdraws prematurely from the first 14 weeks of the study will be asked to complete all study assessments described for the week 14 clinical visit. For patients who withdraw during the continuation phase of the study, the last data collected will be that from the last performed study visit.

For any patient who has withdrawn, the date of withdrawal from the study and the reason for withdrawal will be recorded in the source data and CRF. Adverse Drug Reactions (i.e. AEs that are possibly or probably related to study treatment, see section 11.2), which are unresolved at the time of withdrawal, should be followed until the event has resolved or, if persistent, has been assessed as "chronic" or "stable".

Withdrawn patients should not be re-entered into the study. Additional patients, if available, may be enrolled at the discretion of the Sponsor.

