6.2.4 Post treatment period – 4 weeks without study drug (study week 11-14)

During the post-treatment period study visits will take place at week 12 and 14. A blood sample will be taken for determination of plasma oxalate prior to the dialysis session in week 12 and 14.

At week 14 faecal sample will be taken as well as safety labs.

At each clinic visit the patient will be assessed for the presence or absence of Adverse Events and changes in concomitant medications. At the clinical visit week 14 a physical examination including vital signs will be performed.

Adverse Drug Reactions (i.e. AEs that are possibly or probably related to study treatment, see section 11.1), which are unresolved at the time of week 14 clinic visit, should be followed until the event has resolved or, if persistent, has been assessed as “chronic” or “stable” for patients not participating in the continued treatment period.

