12 STATISTICS

12.1 Statistical methods

Efficacy: The primary endpoint, change in total plasma oxalate from baseline, will be evaluated over time for each patient. Evidence for efficacy will be provided as the combined evaluation of individual case studies. Plasma oxalate levels will be measured on a monthly basis throughout the first 24 months of the continued treatment period and once every 3-4 months during the last 12 months of the continued treatment period. All secondary endpoints will be analysed using the same methodology.

For the primary endpoint the change in total plasma oxalate levels will be based on the average from two baseline measurements (week 2 and week 4) and one measurement every 4th week throughout the first 24 months of the continued treatment period and every 3-4 months during the last 12 months of the continued treatment period.

The change in plasma oxalate during 4 weeks follow-up period after the end of the 6 weeks treatment period with OC5, will be based on one measurement at week 10 and one measurement at week 14. The last observation will be carried forward in case of missing values at week 14 and/or week 10.

Two interim analyses will be performed: The first analysis will be based on patients who complete the first year of continued treatment. The second interim analysis will be based on all study data obtained up to 24 months. Both interim analyses will evaluate all captured efficacy and safety parameters.

The individual changes in plasma oxalate per week will also be calculated as an average slope using regression of plasma oxalate by week.

The study involves a small number of patients and natural history data on changes in total and free plasma oxalate for this population is limited. Response to treatment is likely to vary depending on the baseline plasma oxalate level, individual hepatic oxalate production and age of each patient. Accordingly, the sample size is not based on assumptions of efficacy outcome and statistical power, and the definition of analysis populations is not applicable. Any inferences from the data will be based on clinical relevance rather than statistical significance.

Safety: The safety will be summarised using descriptive statistics based on frequency, seriousness and severity of treatment emergent AEs. Clinically relevant changes in safety laboratory parameters will also be summarised.

All statistical analyses will be further defined in a Statistical Analysis Plan.

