5.2 Secondary endpoint(s)

The secondary endpoints are the following:

- Change from baseline in free plasma oxalate level during OC5 treatment.
- Change in total plasma oxalate levels from week 10 to week 14, following the 4 week off-treatment period.
- Change from baseline in number of *O. formigenes* in faeces during OC5 treatment.
- Change from baseline in echocardiography parameters during OC5 treatment as measured by Speckle Tracking Echocardiography and traditional echocardiography.

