6 STATISTICAL ANALYSIS

6.1 General considerations

All evaluations will be explorative in nature, unless stated otherwise. There will be no formal statistical significance testing.

Raw data (in listings) will be presented in the same precision as received. Appropriate rounding will be performed for the summary statistics: arithmetic mean, median, SD (standard deviation) and two-sided 95% confidence limits will be presented with one more decimal than the original data; minimum and maximum values will be presented with the same precision as the original data. In special cases, e.g. after conversion of data, the number of decimals will be determined based on relevance. In frequency tables, percentages will be presented with 1 decimal unless otherwise stated. P-values will be presented with 3 decimals, and those smaller than 0.001 will be replaced by <0.001.

Descriptive statistics presented in summary tables for continuous variables will be the number of non-missing observations (n), arithmetic mean, SD, SE, median, Q1 and Q3, minimum and maximum. All plots will be created using scheduled protocol time or visit on the x-axis. Mean plots will be presenting mean +/- SE. For qualitative data, frequency counts and percentages will be determined. The denominator used when calculating percentages will be the number of subjects in the applicable analysis population.

Baseline is generally defined as the last non-missing and valid measurement/assessment before first dose of study drug. Unscheduled measurements are excluded as baseline value, unless otherwise specified. Change from baseline is calculated as the value at a specific time point minus the value at baseline. For this study, the following definitions are used to define the baseline measurement:

Vital signs: The screening value is used as baseline.

Plasma oxalate: The primary baseline is defined as an average of the available baseline measurements at weeks 2 and 4 (i.e. Visits 2 and 3 respectively). If one baseline measurement is missing for plasma oxalate, the remaining value will be used as baseline value. An additional baseline is the week 10 (Visit 6) assessment of plasma oxalate levels which will serve (only) as a baseline for the assessment of the change in plasma oxalate levels following the 4 week off-treatment period (secondary endpoint). For analyses in the CT phase of the study, a third baseline is defined, being the week 14 value at week 14 of the initial TRT phase.

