 - If start day is missing, it will be set to the first day of the start month.
 - If both start day and month are missing, then day and month are imputed with the first month and the first day of that month of the available year.
- If end date is completely missing and ongoing is not applicable, then end year is study treatment year-1, end month is the same as the month of the reference date (i.e. the first dose date), and end day is day+1 of that month.
- If the end year is available and the difference between the year of first treatment and the end year of MH is larger than 1 year, then the following applies:
 - If both end month and end day are missing, then the end date will be imputed as 31 December of the available year.
 - If only end day is missing, then the end date will be imputed as the last day of the available month.
- If the end year is available and the difference between the year of first treatment and the end year of MH is 1 year, then the following applies:
 - If month and day are both missing, then month is set to the month of the reference date (i.e. the first dose date), and end day is set to the day of the reference date+1.
 - If only day is missing and month is the same as the month of the reference date, (i.e. the first dose date), then end day is set to day+1 of that month.
 - If only day is missing and month is different from the month of the reference date, (i.e. the first dose date), then end day is set to the last day of the available month.
- If the difference between the year of first treatment and the end year of MH is 0, then the following applies:
 - If both end day and month are missing, then month is imputed with the month of the reference date (i.e. first dosing date) and the end day is set to day-1 of that month, unless the day of the reference is the first day of the month, in which case end day will be set to the same day.
 - If only end day is missing, then the day will be set to the last day of the available month.

For untreated patients, it is not possible to determine MH in the year prior, as there is no reference date (i.e. first dosing date) available.

Plasma Oxalate during 4 -week treatment-off period

In case of missing values for week 10, 12 or 14, the method of LOCF will be applied to calculate CFB values.

Other

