6.6.2 Secondary endpoint

All secondary endpoint analyses will be performed for the FAS only, unless specifically stated that mFAS will also be used. All secondary endpoint analyses will be done on the overall treatment period, unless otherwise specified.

Free plasma oxalate

Change in free plasma oxalate level during OC5 treatment will be analyzed descriptively (tables and plots) as described for the primary endpoint.

Total and free plasma oxalate levels from week 10 to week 14

After 6 weeks of treatment, there is a 4 week off-treatment period scheduled. Change in total and free plasma oxalate levels following the 4 week off-treatment at week 12 and 14 will be calculated as the value at visit 12 or 14 minus the visit value at week 10. Summary statistics of the measurements will be presented on a per-visit basis. Both the actual value as well as the change from baseline value will be presented for the FAS. For handling missing data in summary statistics for CFB values, see section [6.2](#).

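### For a patient who withdraws before week 14, the rules can enter an on-drug or too-early sample, or an LOCF zero, as the change after 4 weeks off OC5

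*Protocol*

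**What the plan says.** **Withdrawal.** Under Protocol 7.3, a patient who leaves in the first 14 weeks "will be asked to complete all study assessments described for the week 14 clinical visit". The section does not say whether this happens on leaving or at calendar week 14. Neither Protocol Table 4 nor SAP Table 1 has an early-termination column. Plasma oxalate is among the week 14 assessments.

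**Off-treatment period.** Dosing covers study weeks 5 to 10 and the drug-free period weeks 11 to 14. Protocol 6.2.4: "During the post-treatment period study visits will take place at week 12 and 14".

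**Endpoint.** SAP 5.2 lists the secondary endpoint "Change in total plasma oxalate levels from week 10 to week 14, following the 4 week off-treatment period". SAP 6.6.2 states that the change "will be calculated as the value at visit 12 or 14 minus the visit value at week 10". That section also says "Summary statistics of the measurements will be presented on a per-visit basis" and uses the FAS, which SAP 3.1.1 defines as every dosed patient.

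**Missing values.** SAP 6.2: "In case of missing values for week 10, 12 or 14, the method of LOCF will be applied to calculate CFB values". Protocol 12.1 has a similar rule: "The last observation will be carried forward in case of missing values at week 14 and/or week 10".

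**Time axis.** SAP 6.1: "All plots will be created using scheduled protocol time or visit on the x-axis". This sentence is about plots. For the per-patient regressions, SAP 6.6.1 names only time as the regressor and Protocol 12.1 only week.

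**The concern.** The week 10 to 14 change is meant to show what happens to plasma oxalate when OC5 is stopped. The study is open-label with no control arm, so this is its planned on/off comparison. The comparison is informative only if the later value was taken about 4 weeks after the last dose and the earlier one at the end of dosing. No analysis rule requires either. The calculation goes by label, sets no condition on actual date or days off drug, and fills gaps by LOCF in every dosed patient. A patient who never had the 4-week drug-free interval can therefore still contribute a change, and that change will tend to be near zero. With about a dozen patients and no formal testing, the descriptive mean is what readers will use, so a few such patients matter.

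**Working it through.** The plan has no figure of its own to reproduce: there is no powered sample size, and no rebound size is assumed.

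**Step 1: one patient, each reading.** Take a patient who leaves at week 8 while on OC5, with samples at weeks 2, 4, 6 and 8. The documents do not say how the exit sample is stored.

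| Handling of the exit sample | Week 10 value | Week 14 value | Change obtained |
|---|---|---|---|
| Taken on leaving, stored as week 14 | LOCF, last on-drug value | On-drug exit sample | Difference of two on-drug values, expected near 0 if levels are steady |
| Taken on leaving, not stored as week 14 | LOCF, last on-drug value | LOCF, same value | Exactly 0 |
| Patient returns at calendar week 14 | LOCF, on-drug value | Observed, about 6 weeks off drug | Not a 4-week change |

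None of these is a change over 4 weeks off drug. In the first row the missing-data rule is not triggered for week 14, because week 14 is not missing.

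**Step 2: leavers in weeks 11 to 13.** These patients are off drug, but for less than 4 weeks. If the exit sample is stored as week 14 and the rebound is linear (assumption), it captures 1/4 = 25%, 2/4 = 50% or 3/4 = 75% of the 4-week change at 1, 2 or 3 weeks off. If it is not stored as week 14, LOCF carries the week 10 or week 12 value to week 14.

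**Step 3: effect on the mean.** Inputs:

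- Treated patients: 12 (Protocol 11.5.1.2).
- Patients entering continued treatment: 8 (same section).
- Upper bound on patients who left before completing week 14: 12 − 8 = 4.
- D: the true 4-week off-drug change, not given, so results are fractions of D.

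If k of the 12 contribute 0 and the rest contribute D on average, the mean is D × (12 − k)/12.

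| k | Mean as a fraction of D | Too small by |
|---|---|---|
| 0 | 12/12 = 1.000 | 0% |
| 1 | 11/12 = 0.917 | 8.3% |
| 2 | 10/12 = 0.833 | 16.7% |
| 3 | 9/12 = 0.750 | 25.0% |
| 4 | 8/12 = 0.667 | 33.3% |

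A leaver in weeks 11 to 13 does less harm under Step 2. At 2 weeks off, for example, one such patient removes 0.5/12 = 4.2% of D.

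**Step 4: slopes, conditional.** Use constructed oxalate values 100, 100, 80, 80 µmol/L for the week 8 leaver.

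- At true weeks 2, 4, 6, 8: Sxy = −80, Sxx = 20, slope −80/20 = −4.00 per week.
- With the last sample placed at week 14: Sxy = −140, Sxx = 83, slope −140/83 = −1.69 per week.

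The second slope is 1 − 1.69/4.00 = 58% too small. This is one invented patient, and it arises only if nominal week is used for the exit sample.

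**The case against.** The strongest reply is that much of the damage depends on things the documents do not say.

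- **Label and timing.** A reader might infer that on-drug samples are definitely scored as week 14 whenever patients leave. Protocol 7.3 says which assessments are requested, not when or under which visit they are recorded, and the CRF is not among the documents reviewed. This stands, so the wording has to be *can be counted*. It does not rescue the endpoint, because the alternative label leads to an LOCF change of 0.
- **Number affected.** The 4 patients who did not continue are not 4 withdrawals. Continuation was optional and depended on the investigator's view of benefit (Protocol 6.1), so all 4 may have completed week 14 properly. This stands.
- **Slopes and primary endpoint.** A reader might infer from the scheduled-time rule that the regressions are distorted too. That rule covers plots only, and the SAP does not say whether regression time is nominal or actual. Distortion there is possible but not shown.
- **Other week 14 summaries.** SAP 6.7.2 and 6.7.3 keep unscheduled laboratory and vital-sign data out of the summaries, so an exit visit recorded as unscheduled would not enter them. SAP 6.6.1 and 6.6.2 state no such rule for plasma oxalate.
- **Safeguards.** The withdrawal date is recorded (Protocol 7.3), visit dates are listed (SAP 6.8.1), and a pre-lock meeting considers protocol deviations (SAP section 4). In so small a study someone may notice. But leaving as 7.3 permits is not clearly a deviation, and no rule tells the meeting what to do with the value.

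**Conclusion.** The concern holds as a gap in a descriptive secondary endpoint. For a patient who leaves during dosing, neither way of storing an exit sample taken on leaving yields a 4-week off-drug change. For one who leaves in weeks 11 to 13, a shorter interval can count as 4 weeks. The bias is toward no change: 8.3% to 33.3% of the mean for 1 to 4 affected patients. That range assumes that all 12 treated patients enter the summary, that affected patients contribute 0, and that the others share the same average change. The true count is not given and may be zero, in which case nothing is lost.

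It would go too far to say that the primary endpoint is biased, or that a planned test of stopping OC5 is invalid. The time variable in the regressions is unspecified, and SAP 6.1 rules out formal testing. The week 14 baseline for continued treatment is also untouched, because withdrawn patients do not enter that phase.

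**What to change.** In SAP 6.1, 6.2 and 6.6.2:

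1. Assign early-termination samples to the week of their actual date, and to on- or off-drug status from the last-dose date.
2. Include a patient in the week 10 to 14 change only with an observed end-of-treatment value and an observed value inside a prespecified window around 4 weeks after the last dose.
3. Do not use LOCF to fill weeks 10, 12 or 14 for this endpoint, and align Protocol 12.1. Without this step, re-dating an on-drug sample simply lets LOCF put the zero back.
4. List excluded samples at their actual week.
5. State in SAP 6.6.1 that the regressions use actual time.

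The summary then estimates D in patients who really had about 4 weeks off drug, provided that they are representative of the treated group.

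Cost: SAP wording, a matching change in Protocol 12.1, and one visit-mapping step. No new data should be needed, since visit dates are already listed (SAP 6.8.1) and treatment start and stop dates already feed the compliance calculation (SAP 6.8.2). The downside is that n for this summary may fall slightly.

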8 TREATMENT OF PATIENTS

8.1 Description of study treatment

The study drug consists of OC5 as the active treatment. The study drug is supplied as enteric-coated capsules. One capsule shall be administered orally with water twice daily with breakfast and dinner. For patients using a gastric tube the capsules may be administered through the tube. The study product is described in more detail in section 9.

8.2 Concomitant medications

Any medications including over-the-counter medications or herbal supplements will be recorded as concomitant drug therapy on the case report form. Patients will continue any medications they are receiving at study entry for underlying medical conditions and the medications will be recorded at screening and changes will be noted throughout the study.

